A key barrier faced by elderly Singaporeans in reading and understanding their PMLs is the language commonly used on them, English. A study of a national sample of elderly Singaporeans found that despite 69% being unable to read English, their PMLs were mostly only in English (81%). This discrepancy places the elderly at risk of medication errors, non-adherence, and side effects. At the same time, many elderly Singaporeans who cannot read English can read another official language (Mandarin Chinese/Malay/Tamil). This highlights a **direct and** innovative approach to make existing PMLs patient-centric, i.e., add another preferred language – bilingual PMLs. A study led by the project mentor showed that bilingual PMLs lead to a substantial increase in understanding of PML content among the elderly, supporting its real-world utility. And, patient feedback collated by the project Co-Is (SGH pharmacists) strongly suggests the need for bilingual PMLs. However, adoption of bilingual PMLs in Singapore has been slow. One reason is the lack of evidence for their positive impact on important medication-related outcomes, i.e., medication management self-efficacy and medication adherence. The proposed study will provide rich preliminary data that will enable the conduct of a larger RCT on the impact of bilingual PMLs on these very medication-related outcomes.

Conceptual Framework: Our framework focuses on the relationship between attainment of knowledge (medication knowledge via PMLs), medication management self-efficacy and engagement in self-care behaviours (i.e. medication taking behaviour) as a process that ultimately affects our key outcome, medication adherence. (Figure 1)

Attainment of knowledge: Cognitive processes (i.e., perception, memory, problem solving, etc.) generally subsume the concept of understanding. In investigating PML understandability, understanding has been defined as the capacity to describe – using one's own words (i.e., more than simply reading) – how a medication should be taken. In context of our study, bilingual PMLs will facilitate understanding among

the elderly, resulting in attainment of medication knowledge. Research shows that lack of knowledge is likely to affect individual's self-

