Need for rigorous PML intervention studies: A recent review on the impact of improved PMLs concluded that intervention studies that test PML improvements in a rigorous manner are lacking. It also recommended that future studies should extend research to outcomes more proximal to medication taking – medication adherence and medication management self-efficacy. In Singapore, the only published PML intervention did show bilingual PMLs (vs English PMLs) to increase PML understanding. However, it, again, did not assess medication adherence and medication management self-efficacy. Thus, rigorous intervention studies that assess the impact of improved PMLs on a range of medication-related outcomes are needed.

Our proposal is the *first step* towards a well-informed, rigorous intervention study or RCT that will provide concrete evidence on the impact of the provision of bilingual PMLs on key medication-related outcomes – medication adherence, medication management self-efficacy, and PML understanding. The experience gained, and data collected, through the conduct of the 2 pilot trials, funded through the current proposal, will allow us to choose the optimal trial design, and refine protocols for recruitment, engagement and retention of study participants for the larger RCT as well as determine variability in outcomes so that the larger RCT is appropriately powered to detect meaningful differences in the outcomes – an immediate output of our proposed project will be a grant proposal to a national level grant mechanism for the conduct of the larger RCT. Eventually, the 2 pilot trials, and the subsequent larger RCT, will contribute to implementing patient-centered PMLs.

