#### 2. HYPOTHESIS AND OBJECTIVES

Since the proposed study will collect preliminary data for informing the larger RCT, it does not aim to detect a significant difference in the trial outcomes in either pilot trial. Rather, its specific aims are:

AIM 1. To assess the feasibility of administering the intervention in the 2 "pilot" RCT versions. The proposed formative study will inform which of the 2 pilot trials will be scaled up and tested in the larger RCT. It will also result in finalization of the intervention and measurement material. AIM 2. To refine protocols for study participant recruitment, engagement and retention. AIM 3. To gain experience with and refine measurement of the medication-related outcomes.

A key outcome, medication adherence, will be measured using several approaches – self-report (ARMS; MedTake Assessment), which is easier and cheaper, and objective (pill count; electronic medication packaging [EMP]), which is tedious and expensive – during the 2 pilot trials. Comparison of the various approaches against the EMP (the most objective approach) will inform the choice of the measurement approach to be used for medication adherence in the larger RCT.

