#### 5. STUDY DESIGN AND PROCEDURES/METHODOLOGY

This is a 2-arm open-label parallel-group RCT with 2 versions (Pilot Trial A, and Pilot Trial B). A total of 40 eligible patients, after informed consent, will be randomized (1:1; block randomization, block of 4) in the DMC pharmacy to either Pilot Trial A or Pilot Trial B (Figure 2).

\* Study procedures have been modified slightly in view of prevailing COVID-19 control measures. Please refer to section 5.1.1 for a detailed methodology.

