#### 5.1 Study Design

Briefly, in Pilot Trial A, all will be first given the usual English PML for their new medication. There may be non-standardized, ad-hoc noting on the PML by the pharmacy staff when participant is deemed not able to understand the English PML. All content of the non-standardized, ad-hoc noting including pictures drawn will be recorded. Then, *at 2 weeks post-recruitment*, their baseline level of the 3 medication-related outcomes (w.r.t. the new medication) will be gauged, after which they will be *randomized* (1:1; block randomization, block of 4) to one of 2 PMLs (Bilingual [intervention] or English [usual care]) at their home. Follow-up assessment of the 3 medication-related outcomes will be also be done at 2 weeks post-randomization at their home.

In Pilot Trial B, participants will be *randomized* (1:1; block randomization, block of 4) *just after recruitment* to one of 2 PMLs (Bilingual [intervention] or English [usual care]) in the DMC pharmacy. There may be non-standardized,ad-hoc noting on the PML by the pharmacy staff when participant is deemed not able to understand the English PML. All content of the non-standardized, ad-hoc noting pictures drawn will be recorded. The 3 medication-related outcomes will be assessed at 2 weeks post-randomization at their home.

All participants will receive their usual medical care, and usual medication counselling at the DMC pharmacy for all their medications. All medications, other than the new oral medication (which made them eligible, and whose PML will be intervened upon), will be dispensed with usual English PMLs.

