# 8.2. Statistical and Analytical Plans

As we are conducting 2 "pilot" versions of a RCT, most analyses will be descriptive and exploratory. In both pilots, trial outcomes will be summarized using measures of central tendency and dispersion (e.g., mean and standard deviation). In Pilot Trial A, significant difference in change, from baseline to 2 weeks post-randomization, in the 3 medication-related outcomes between the 2 arms will be assessed using t-test (for continuous variables, e.g. difference in change in ARMS

scores or MUSE scores) or chi-square test (for categorical variables, e.g. difference in change in % with complete PML understanding or % with complete adherence as per EMP). In Pilot Trial B, significant difference, at 2 weeks post-randomization, in the 3 medication-related outcomes between the 2 arms will be assessed using t-test (for continuous variables, e.g. difference in the ARMS scores or MUSE scores) or chi-square test (for categorical variables, e.g. difference in % with complete PML understanding or % with complete adherence as per EMP). For agreement between medication adherence assessed using EMP and that assessed using the 3 other approaches, Bland-Altman plots (adherence considered as continuous) and Cohen's kappa43.45 ( $\varkappa$ ; adherence considered as categorical) will be used. While our findings will only provide a general sense of the intervention impact, they will primarily inform which measures to use for the subsequent RCT and for determining its optimal sample size. We will also tabulate participation rates and loss to follow-up.

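### Section 8.2 names only significance tests for comparing the arms, although Section 2 disclaims that aim; report differences with 95% CIs instead

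*Protocol*

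**What the plan says.** Section 2 sets the aims as feasibility, refinement of recruitment and retention, and experience with measuring the outcomes. It says of the study that "it does not aim to detect a significant difference in the trial outcomes in either pilot trial".

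Section 1 adds that the data should "determine variability in outcomes so that the larger RCT is appropriately powered to detect meaningful differences in the outcomes". Section 8.2 repeats the purpose, saying of the findings that "they will primarily inform which measures to use for the subsequent RCT and for determining its optimal sample size".

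Section 8.2 opens by saying that "most analyses will be descriptive and exploratory" and plans means and standard deviations in both pilots. For the comparison of arms it then names only tests:

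- Pilot Trial A: a t-test or chi-square test for a significant difference in change from baseline to 2 weeks after randomization.
- Pilot Trial B: "significant difference, at 2 weeks post-randomization, in the 3 medication-related outcomes between the 2 arms will be assessed using t-test", or a chi-square test for categorical outcomes.

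The remaining analyses are Bland-Altman plots and kappa for agreement between adherence measures, and tables of participation and loss to follow-up. None of these compares the arms. No estimated between-arm difference and no confidence interval is named. Section 8.1 states that no sample size estimation was done.

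**The concern.** The named between-arm analysis answers a question that the study says it is not asking. The stated purpose is to learn about variability, measures and the sample size of a later trial. A test result at about 10 per arm contributes almost nothing to that, and a non-significant one is easily misread as evidence of no effect. An estimate with its interval shows directly which effects remain plausible, and that is what a planner of the larger RCT can use.

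**Working it through.** The protocol states no power, alpha, effect size, SD or dropout, so there is no figure of its own to reproduce. The effect sizes, SD ratio and proportions below are assumptions; so are two-sided 0.05 and no dropout.

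**Arm size.** Section 5 says that the 40 patients "will be randomized (1:1; block randomization, block of 4) in the DMC pharmacy to either Pilot Trial A or Pilot Trial B", and Section 5.1 randomizes 1:1 again within each pilot: 40 / 2 / 2 = 10 per arm.

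**t-test power** (noncentral t, df = 2 × 10 − 2 = 18, noncentrality d × √(10/2), where d is the difference in SD units):

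| d | Power at 10 v 10 |
|---|---|
| 0.5 | 19% |
| 0.8 | 40% |
| 1.2 | 72% |
| 1.5 | 89% |

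Power reaches 80% at d = 1.325, so about 1.33 rounded up.

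**Chi-square power** (Pearson, no continuity correction, exact enumeration at 10 v 10): 25% for 30% v 60%, 62% for 30% v 80%, 81% for 20% v 80%.

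**What an interval would show.** The 95% half-width for a mean difference is t(0.975; 18) × SD × √(2/10) = 2.101 × 0.447 SD = 0.94 SD. For a risk difference at 30% v 60%, the simple large-sample half-width is 1.96 × √((0.3 × 0.7 + 0.6 × 0.4)/10) = 1.96 × √0.045 = 0.42, or 42 percentage points. Both are wide, but the width is visible to the reader; a non-significant p-value hides it.

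**Optional: a more precise 2-week SD.** In Pilot Trial A, "all will be first given the usual English PML for their new medication", and everyone is measured at 2 weeks after recruitment before the label arm is disclosed (Section 5.2). Pilot Trial B is randomized just after recruitment, so its 2-week assessment falls at the same time. Pooling with separate group means over Pilot A at 2 weeks (n = 20) and the two Pilot B arms (n = 10 each) gives 19 + 9 + 9 = 37 df, against 9 + 9 = 18 df within Pilot B. The 95% limits for an SD, as multiples of the estimate, are √(df/χ²):

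- 18 df: √(18/31.53) to √(18/8.23) = 0.76 to 1.48
- 37 df: √(37/55.67) to √(37/22.11) = 0.82 to 1.29

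If the larger RCT is sized for 80% power on the point SD, true power falls below 70% when χ² < df × r², with r = (0.524 + 1.960)/(0.842 + 1.960) = 0.887. That probability is 28% with 18 df and 18% with 37 df.

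Using only the English-label groups (19 + 9 = 28 df) gives 22%, but only if the bilingual arm has the same SD. If the bilingual SD is 1.25 times the English SD, the mean variance of the two arms is (1 + 1.25²)/2 = 1.28 times the English variance, and the probability becomes 55%.

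**The case against.** The strongest reply is that the conflict is mild. Not aiming to detect a significant difference is not the same as promising to run no test. Section 8.2 plans means and SDs before any test, calls most analyses exploratory, and closes by saying that the findings give only a general sense of the impact. For continuous outcomes in Pilot B, arm means and SDs with their n would let a reader compute the interval. All of this stands, and it limits the weight of the point. It does not remove it: the text still names significance tests as the sole between-arm analysis and nowhere names the estimate or its precision.

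Three stronger readings are tempting and are not supported.

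- A reader might infer that the choice between pilots, or the go-ahead for the larger RCT, hangs on an underpowered test. No decision in the protocol depends on a p-value.
- A reader might call the tests worthless. Section 1 reports from an earlier study that "bilingual PMLs lead to a substantial increase in understanding of PML content among the elderly", so a large effect on that outcome is possible, and power is fair if d is 1.2 to 1.5.
- A reader might treat the absence of a pooled SD as an error. Section 8.2 says nothing wrong on this, its wording does not exclude pooling, and the choice of SD may properly be left to a statistical analysis plan. The gain is also narrow: it covers continuous 2-week outcomes only and depends on a common SD across labels.

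**Conclusion.** The point holds as a mismatch between the stated aim and the named analysis, of minor to moderate weight. The mismatch is in the text and needs no calculation. The calculation shows why it matters: at about 10 per arm the tests have little power unless the effect exceeds roughly one SD, so a non-significant result would not inform the larger RCT. The figures assume 10 evaluable patients per arm, two-sided 0.05 and, for the t-test, normal outcomes with equal SDs; any dropout lowers power further. The pooled SD is a possible improvement and not a defect of the plan.

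**What to change.** In Section 8.2, replace the assessment of a significant difference with the estimated between-arm difference and its 95% CI: difference in change for Pilot A, difference in the 2-week value for Pilot B, and a risk difference with CI for categorical outcomes. If p-values are kept, label them secondary and exploratory. The cost is wording and minor analysis work; no new data, visits or patients are needed.

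Optional addition: for continuous 2-week outcomes, report beside the within-pilot SD an SD pooled with separate group means over Pilot A at 2 weeks after recruitment and both Pilot B arms, with its 95% interval. State three limits with it:

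- It assumes a common SD across labels.
- Sizing a two-arm RCT on an English-only SD needs the same assumption.
- It does not inform the SD of change in Pilot A, which would be needed if that design is scaled up with a change-score analysis.

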#### 5.1.1 Modified Study Design In View Of COVID-19

In view of COVID-19 restrictions imposed as of 16 August 2021, a portion of the Main Questionnaire will be done via phone call instead of fully relying on home visits. The study staff

will conduct a home visit to complete the remaining questions from the Main Questionnaire and collect data from the Rx  $Cap^{TM}$  bottles, with a time limit of 20 minutes to keep participants and staff safe.

Additionally, should any participants be subjected to COVID-19 Stay Home Notices or Quarantine Orders, participation will immediately be forfeited for the safety of participants and study staff. Retrieval of the Rx CapTM bottle and delivery of remaining medicines will be arranged in a proper manner in accordance to any guidelines set by the SGH Research Office and MOH.

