#### 5.2.1 Measurements

Medication adherence: It will be measured in 4 different ways:

- 1. Adherence to Refills and Medications Scale (ARMS): A validated self-reported medication-adherence scale intended for patients with chronic diseases. The 12-item questionnaire consists of 2 sub scales adherence to refilling prescriptions and adherence with taking medications. Each item is structured using the Likert scale, with the following response options and corresponding scores: "none" (score of 1), "some" (score of 2), "most" (score of 3), or "all of the time" (score of 4). The range of possible total scores is 12 to 48. Lower scores indicate better adherence.
- 2. MedTake Assessment: A self-reported measure, recommended by Ministry of Health, Singapore for pharmacy staff when they provide pharmaceutical care services, that assesses patient adherence and knowledge to dose, dosage, indication, food or water coingestion, and regimen. A composite score (0–100%; higher ~ better) summarizes patient's ability to take medication safely.
- Pill count: A pill count, in context of the new oral medication, will be done.
  % adherence= ((quantity dispensed)-(quantity remaining))/((prescribed number of pills per day)×(no.of days between dispensing date and interview))

Electronic medication packaging [EMP]: All participants will be dispensed their new oral

medication in a Rx CapTM medication bottle (www.rxcap.com), whose Rx CapTM Bluetooth smart cap will automatically track medication usage every time it is opened. Project staff will sync participants' data, collected and stored within the Smart Cap, at each home visit, and import it to the Rx CapTM Engage platform for analysis. Continuous (% adherence to prescribed regimen; 0-100%) and categorical variables (not at all; partially; fully) for medication adherence will be derived. Rx CapTM medication bottle is not being used in standard clinical practice yet and it is used for this proposed research only. To our best knowledge, Rx CapTM medication bottle is not validated for use clinically yet.

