# 7.2. Data Entry and Storage

All data with personal identifiers will be encrypted with password-protection. All physical research data including consent forms, data entry forms will be stored in locked cabinets at SGH. All soft copy research data will be coded, with participants' identifiers stored separately from research data, and only available on computers within the institution. Only de-identified data will be shared with study team members for data analysis and only the investigators and authorized personnel (principal investigator, co-investigators and research assistant) directly involved with the study will have access to the data. After study completion, research data will be stored on institution computers and remain password-protected, for a minimum of 7 years after completion of research study or date of publication of the research using the research data, whichever is later.

The Rx CapTM bottle measures patients medication adherence (Adherence is considered "met" when the new oral medication is taken based on both prescribed number of times per day and prescribed time of the day), each participant will be given 1-2 Rx CapTM pill tracker bottles. The electronic cap of the pill tracker records the date and time when the patient opens the vial to take his/her medication. This bottle does not collect any personal identifiers. A Rx CapTM account would be created for each participant. However, these accounts will be created by the study team using non-identifiable user information (i.e., "dummy" email addresses/usernames). As such, no personal identifiers will be stored in third-party databases.

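### Bland-Altman limits are planned for EMP against ARMS, although the two scores differ in unit and direction and no conversion is stated

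*Protocol*

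**What the plan says.** Protocol section 5.2.1 lists four adherence measures: ARMS, MedTake, pill count and EMP. Section 8.2 compares EMP with each of the others: "For agreement between medication adherence assessed using EMP and that assessed using the 3 other approaches, Bland-Altman plots" for adherence as a continuous variable, and Cohen's kappa for adherence as a categorical one.

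The scales in section 5.2.1 are:

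- **EMP**: percent "adherence to prescribed regimen; 0-100", so higher is better.
- **ARMS**: a 12-item sum. "The range of possible total scores is 12 to 48. Lower scores indicate better adherence". It "consists of 2 sub scales adherence to refilling prescriptions and adherence with taking medications".
- **MedTake**: a 0 to 100% composite, higher better, that "assesses patient adherence and knowledge to dose, dosage, indication, food or water coingestion, and regimen".
- **Pill count**: a percentage built from "quantity dispensed)-(quantity remaining", divided by the number of pills prescribed for the period.

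Section 7.2 adds that EMP adherence is met when the medication is "taken based on both prescribed number of times per day and prescribed time of the day".

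Nothing in the protocol reverses or rescales ARMS. Where section 8.2 names ARMS, in the t-tests, it refers to the scores as they stand. Section 2 says the comparison with EMP will inform which adherence measure the larger RCT uses, and section 8.2 repeats that purpose.

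**The concern.** A Bland-Altman plot analyses the difference between two measurements of the same quantity, in the same unit and running the same way. Pill count meets the unit and direction requirements against EMP, and MedTake at least shares EMP's range and direction. ARMS shares neither unit, range nor direction. Its total also includes refill behaviour, which a record of bottle openings does not capture.

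If the raw scores are subtracted, the reported bias and limits come mainly from the scales and from how much EMP varies between patients. They say little about how well ARMS reflects EMP. Choosing the adherence measure is one of the pilot's stated purposes, and section 2 describes self-report as the easier and cheaper route. ARMS could be wrongly dropped, or its continuous comparison could simply be unusable.

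**Working it through.** The protocol states no agreement figure, and section 8.1 gives no sample size calculation, so there is no planned number to reproduce. The check uses the stated ranges first and then labelled assumptions.

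**1. Stated ranges only.** Let D = EMP - ARMS.

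| Patient | EMP | ARMS | D |
|---|---|---|---|
| Best on both | 100 | 12 | +88 |
| Middle of both | 50 | 30 | +20 |
| Worst on both | 0 | 48 | -48 |
| Contradictory | 12 | 12 | 0 |

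The first three patients are fully concordant, yet they span 88 - (-48) = 136 points. The fourth has 12% adherence by EMP and the best possible ARMS score, and plots as perfect agreement.

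**2. Exact mirroring.** Assume ARMS = 48 - 0.36 × EMP, where 0.36 = (48 - 12)/100. Then D = 1.36 × EMP - 48, and the half-width of the 95% limits is 1.96 × 1.36 × SD(EMP). The protocol gives no SD for EMP. At assumed values of 10, 20 and 30 the half-width is 26.7, 53.3 and 80.0, although ARMS tracks EMP perfectly.

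**3. Removing random error from ARMS.** Let ARMS = 48 - 0.36 × EMP + e, with e independent of EMP, SD(e) = s, and the scale bounds ignored. Then:

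- Var(D) = 1.36² × SD(EMP)² + s²
- r = -0.36 × SD(EMP) / √((0.36 × SD(EMP))² + s²)
- after rescaling by 100 × (48 - ARMS)/36, the difference from EMP is e/0.36, with half-width 1.96 × s/0.36

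At SD(EMP) = 20:

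| s | r | Half-width, raw | Half-width, rescaled |
|---|---|---|---|
| 8 | -0.67 | 55.6 | 43.6 |
| 5 | -0.82 | 54.2 | 27.2 |
| 3 | -0.92 | 53.6 | 16.3 |
| 0 | -1 | 53.3 | 0 |

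The raw limits hardly move while ARMS goes from moderate to perfect. The same holds at SD(EMP) = 10 (raw 30.9, 28.4, 27.3, 26.7) and at 30 (81.5, 80.6, 80.2, 80.0). The rescaled column is the same at any SD(EMP).

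**4. Holding the ARMS spread fixed.** With SD(ARMS) = 0.36 × 20 = 7.2 and SD(EMP) = 20, the half-width is 1.96 × √(20² + 7.2² - 2 × r × 20 × 7.2). This gives 41.7 at r = 0, 47.8 at r = -0.5 and 53.3 at r = -1. Here the raw limits widen as ARMS tracks EMP better.

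**5. Precision of a rank correlation instead.** Using Fisher's z with SE = √((1 + r²/2)/(n - 3)) and an observed r = -0.5, z = -0.549:

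- n = 40: SE = √(1.125/37) = 0.174, 95% CI -0.71 to -0.20
- n = 30 (assumed, after losses): SE = √(1.125/27) = 0.204, 95% CI -0.74 to -0.15
- n = 20 (one pilot alone): SE = √(1.125/17) = 0.257, 95% CI -0.78 to -0.05

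**The case against.** The strongest reply is that section 8.2 does not say raw totals will be subtracted. It says only that adherence is treated as continuous. The same sentence plans kappa, although section 5.2.1 defines adherence categories for EMP alone, so some derived variables must still be specified, and an analysis plan not shown here may do that. It is also fair that the pilot is exploratory, that kappa is planned alongside, that there is no numerical selection rule, and that only one of the three pairs is affected. No data would be lost, since ARMS can be rescaled or correlated at analysis. The SDs used above are illustrative.

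Most of this limits the consequence and leaves the error in place. The only continuous form of ARMS in the protocol is the 12 to 48 total, and the method named for it does not suit that scale. The +88, -48 and zero cases in step 1 need no assumed SD. Kappa does not repair the continuous analysis.

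Two points stand. MedTake also mixes in something other than doses taken, so it needs a caveat of its own. And a correlation answers a question about association, not agreement, with little precision at this sample size.

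**Conclusion.** The concern holds. As written, the Bland-Altman comparison of EMP with ARMS does not measure agreement, and its limits cannot separate a good ARMS from a poor one. That conclusion rests on the scales and directions in section 5.2.1 and on the absence of a conversion. The half-widths of 27, 53 and 80 rest in addition on assumed EMP SDs of 10, 20 and 30 and on a linear mirror between the scales. They illustrate the defect and do not predict this trial's results.

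The defect is confined to one pair in one of two agreement methods within an exploratory pilot. It still deserves correction before analysis, because the comparison feeds directly into the choice of measure for the larger RCT.

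**What to change.** In section 8.2, for ARMS against EMP:

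- Replace the Bland-Altman plot with a Spearman correlation and its 95% CI, or a regression of EMP percentage on ARMS score. Report it as association or calibration, not agreement.
- Use one assessment per participant, since Pilot Trial A participants are assessed twice, and say whether the two pilots are pooled.
- Report the ARMS total and the medication-taking subscale separately.
- If limits of agreement are kept, first convert ARMS by 100 × (48 - ARMS)/36. State that the result is a percentage of the scale range, not of doses: answering 'some' to all 12 items scores 24 and becomes 100 × 24/36 = 66.7%.

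Keep Bland-Altman for pill count and MedTake, with two stated caveats. EMP requires both the number of times and the time of day to be right, whereas the pill count covers quantity only. For illustration, take a once-daily drug over 14 days with every dose taken but 4 at the wrong time. The pill count is 100% and EMP is 10/14 = 71.4%, if each mistimed day is assumed not met. MedTake combines adherence with knowledge. A difference from EMP is therefore not purely disagreement about doses taken.

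The cost is a change of wording and a small analysis of data already planned. The drawbacks are that ARMS has no limits of agreement on its raw scale and that the correlation will be imprecise (step 5 of the working). Numbers may fall below 40 through loss to follow-up or because, under section 5.1.1, for anyone under a Stay Home Notice or Quarantine Order "participation will immediately be forfeited for the safety of participants and study staff".
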